**Table 3: Basal Insulin Dose Adjustment Based on Fasting Glucose Result**

Lowest Average Fasting Plasma Glucose (Pre-Breakfast) Value for 3 Days	Adjust Basal Insulin Dose (Units per Dose)
> 271 mg/dL (> 15.1 mmol/L)	+ 6 U
181 – 270 mg/dL (10.1 – 15.0 mmol/L)	+ 4 U
151 – 180 mg/dL (8.4 – 10.0 mmol/L)	+ 2 U

Lowest Average Fasting Plasma Glucose (Pre-Breakfast) Value for 3 Days	Adjust Basal Insulin Dose (Units per Dose)
131 – 150 mg/dL (7.3 – 8.3 mmol/L)	+ 1 U
71 – 130 mg/dL (> 3.9 – 7.2 mmol/L) (Target Level)	Maintain Current Dose
56 – 70 mg/dL (3.1 – 3.9 mmol/L)	- 2 U
< 56 mg/dL (< 3.1 mmol/L)	- 4 U

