7.4 Exploratory

1) Continuous Glucose Monitoring Device Day of Wear

The Day of wear will be defined as starting exactly $(x-1)*24$ hours and ending $x*24$ hours after the time of the first assessment at the given visit, where x is the Day of wear from 2 to 8 days.

Sponsor: Gan & Lee Pharmaceuticals, USA Corporation
Protocol no: GL-GLAT2-3002

Statistical Analysis Plan
Version Date: 16-Nov-2020

2) Time in hypoglycemia

The time in hypoglycemia will be defined using the CGM data from days 2 through 8 of wear at each of the 3 visits where CGMs are applied as the sum of the time where the glucose value is ≤ 3.0 mmol/L.

$$\sum_{i=1}^{n_T} I_{GC_i}(t_{i+1} - t_i)$$

where I_{GC_i} represents the indication of whether or not the glucose concentration at time i is ≤ 3.0 mmol/L, t_i represents the i^{th} time point (the difference between each time point will be 15 minutes), and n_T represents the number of time points for a given subject and visit and can vary based on subject and visit.

3) Time in hyperglycemia

The time in hyperglycemia will be defined using the CGM data from days 2 through 8 of wear at each of the 3 visits where CGMs are applied as the sum of the time where the glucose value is ≥ 8.9 mmol/L.

$$\sum_{i=1}^{n_T} I_{GC_i}(t_{i+1} - t_i)$$

where I_{GC_i} represents the indication of whether or not the glucose concentration at time i is greater than or equal to 8.9 mmol/L, t_i represents the i^{th} time point (the difference between each timepoint will be 15 minutes), and n_T represents the number of time points for a given subject and visit and can vary based on subject and visit.

4) Time in euglycemia

The time in euglycemia will be defined using the CGM data from days 2 through 8 of wear at each of the 3 visits where CGMs are applied as the sum of the time where the glucose value is >3.0 mmol/L and < 8.9 mmol/L.

$$\sum_{i=1}^{n_T} I_{GC_i}(t_{i+1} - t_i)$$

where I_{GC_i} represents the indication of whether or not the glucose concentration at time i is >3.0 mmol/L and <8.9 mmol/L, t_i represents the i^{th} time point (the difference between each time point will be 15 minutes), and n_T represents the number of time points for a given subject and visit and can vary based on subject and visit.

8. Analysis Sets

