11.7.3.2 Retrospective Time in Hypoglycemia/Hyperglycemia

The time in hypoglycemia/hyperglycemia/euglycemia will be summarized with descriptive statistics at each visit and overall using the SS (Table 6, Analysis 2).

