11.8.1.1 Hypoglycemic AEs based on documentation on the Hypoglycemia CRF page
Hypoglycemic AEs which are only documented on the CRF AE page and for whom the CRF Hypoglycemia page is blank or missing will not be considered in the analyses which are described below.

An additional breakdown of hypoglycemic TEAEs categorized by maximum CTCAE and ADA grade within each SOC and preferred term will be provided (Table 6, Analyses 4 - 8). The analysis will be done for hypoglycemic AEs measured with test methods "Fingerstick" and "Venous Blood Draw" (Table 6, Analyses 5 and 7). Events graded using lowest blood glucose values with test method "Other" will be presented separately (Table 6, Analyses 6 and 8). For this analysis the CTCAE and ADA grades will be derived using information documented on the Hypoglycemia page. Grading will be based on mmol/L unit (mg/dL values will be converted to mmol/L before grading).

Table 7: CTCAE grades for Hypoglycemia (based on lowest blood glucose values documented on the Hypoglycemia page)

SOC	AE Term	Grade 1	Grade 2	Grade 3	Grade 4
Metabolism and nutrition disorders	Hypoglycemia	<3.9 and ≥ 3.0 mmol/L	<3.0 and ≥ 2.2 mmol/L	<2.2 and ≥ 1.7 mmol/L	<1.7 mmol/L;

Table 8: ADA grades for Hypoglycemia (based on lowest blood glucose values and intervention information documented on the Hypoglycemia page)

SOC	AE Term	Grade 1	Grade 2	Grade 3
Metabolism and nutrition disorders	Hypoglycemia	<3.9 and \geq 3.0 mmol/L	<3.0 mmol/L	A severe event characterized by altered mental and/or physical status requiring assistance selected by "Was third party intervention required for this episode of hypoglycemia?" is Yes

On the Hypoglycemia CRF page further details are documented if the answer to the question "Is this a hypoglycemic event?" on the Adverse Event CRF page is Yes. Hypoglycemic TEAEs will be reported using data recorded on both the Adverse Event page and the Hypoglycemia page as follows:

- Severe Hypoglycemia (Table 6, Analysis 9)
- Symptomatic Hypoglycemia (Table 6, Analysis 12)
- Measured Hypoglycemia (Table 6, Analysis 12)

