Metabolism and nutrition disorders	Hypocalcemia	Corrected serum calcium of <LLN - 8.0 mg/dL; <LLN - 2.0 mmol/L; ionized calcium <LLN - 1.0 mmol/L	Corrected serum calcium of <8.0 - 7.0 mg/dL; <2.0 - 1.75 mmol/L; ionized calcium <1.0 - 0.9 mmol/L; symptomatic	Corrected serum calcium of <7.0 - 6.0 mg/dL; <1.75 - 1.5 mmol/L; ionized calcium <0.9 - 0.8 mmol/L; hospitalization indicated	Corrected serum calcium of <6.0 mg/dL; <1.5 mmol/L; ionized calcium <0.8 mmol/L; life threatening consequences
Investigations	Creatinine increased	>1 - 1.5 x baseline; >ULN - 1.5 x ULN	>1.5 - 3.0 x baseline; >1.5 - 3.0 x ULN	>3.0 x baseline; >3.0 - 6.0 x ULN	>6.0 x ULN
Metabolism and nutrition disorders	Hyperglycemia	Fasting glucose value >ULN - 160 mg/dL; Fasting glucose value >ULN - 8.9 mmol/L	Fasting glucose value >160 - 250 mg/dL; Fasting glucose value >8.9 - 13.9 mmol/L	>250 - 500 mg/dL; >13.9 - 27.8 mmol/L; hospitalization indicated	>500 mg/dL; >27.8 mmol/L; life-threatening consequences
Metabolism and nutrition disorders	Hypoglycemia	<LLN - 55 mg/dL; <LLN - 3.0 mmol/L	<55 - 40 mg/dL; <3.0 - 2.2 mmol/L	<40 - 30 mg/dL; <2.2 - 1.7 mmol/L	<30 mg/dL; <1.7 mmol/L; life-threatening consequences; seizures
Metabolism and nutrition disorders	Hyperkalemia	Blood potassium value >ULN - 5.5 mmol/L	Blood potassium value >5.5 - 6.0 mmol/L	Blood potassium value >6.0 - 7.0 mmol/L; hospitalization indicated	Blood potassium value >7.0 mmol/L; life-threatening consequences
Metabolism and nutrition disorders	Hypokalemia	Blood potassium value <LLN - 3.0 mmol/L	Blood potassium value <LLN - 3.0 mmol/L; symptomatic; intervention indicated	Blood potassium value <3.0 - 2.5 mmol/L; hospitalization indicated	Blood potassium value <2.5 mmol/L; life-threatening consequences
Metabolism and nutrition disorders	Hyponatremia	Plasma sodium <LLN - 130 mmol/L	-	Plasma sodium <130 - 120 mmol/L	Plasma sodium <120 mmol/L; life-threatening consequences
Metabolism and nutrition disorders	Hypernatremia	Plasma sodium >ULN - 150 mmol/L	Plasma sodium >150 - 155 mmol/L	Plasma sodium >155 - 160 mmol/L; hospitalization indicated	Plasma sodium >160 mmol/L; life-threatening consequences

Gan & Lee Pharmaceuticals USA PRAHEALTHSCIENCES

Sponsor: Gan & Lee Pharmaceuticals, USA Corporation
Protocol no: GL-GLAT2-3002

Statistical Analysis Plan
Version Date: 16-Nov-2020

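### SAP 7.4 counts sensor glucose above 3.0 and below 3.9 mmol/L as euglycemia, so the CGM time tables cannot show time in the band that SAP Tables 7 and 8 call Grade 1 hypoglycemia

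*SAP*

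**What the plan says.** SAP 7.4 divides sensor glucose on days 2 to 8 of wear into three categories that together cover every value:

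- Time in hypoglycemia: "the sum of the time where the glucose value is ≤ 3.0 mmol/L".
- Time in euglycemia: "the sum of the time where the glucose value is >3.0 mmol/L and < 8.9 mmol/L".
- Time in hyperglycemia: "the sum of the time where the glucose value is ≥ 8.9 mmol/L".

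SAP 11.7.3.2 reports all three: "The time in hypoglycemia/hyperglycemia/euglycemia will be summarized with descriptive statistics at each visit and overall using the SS". Time in hypoglycemia and time in hyperglycemia are listed exploratory endpoints (Protocol 8.8, SAP 6.4). Time in euglycemia is not listed there and appears only in the SAP's definitions and analysis sections.

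SAP 11.8.1.1 grades hypoglycemic adverse events by the lowest glucose on the Hypoglycemia CRF page. Grade 1 is "<3.9 and ≥ 3.0 mmol/L" in both Table 7 (CTCAE) and Table 8 (ADA). SAP Appendix 2 grades laboratory glucose similarly, with Grade 1 hypoglycemia given as "<LLN - 55 mg/dL; <LLN - 3.0 mmol/L".

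The time measure is used once more. SAP 7.3 item 7 classes a hypoglycemic event as persistent if its CGM time in hypoglycemia, as defined in 7.4, is one hour or more. SAP 11.8.1.1 summarizes that classification with the safety results.

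**The concern.** Only the CGM definitions call glucose just above 3.0 mmol/L euglycemia. In the event tables the same band is the lowest grade of hypoglycemia, and SAP 11.8.3.1 reserves Grade 0 for normal laboratory values. Neither document explains the different label.

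Two outputs are affected.

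1. **The CGM time tables.** Time in the Grade 1 band is merged into the normal category. If one product produced more sensor time at, say, 3.5 mmol/L without more time at or below 3.0, none of the three reported times would separate it from time spent at 5 mmol/L. SAP 11.7.3.1 uses the CGM data to look for episodes the subject did not notice, so a reader will want to see the mild end of the range.
2. **The persistence summary.** A reported event whose sensor values stay between 3.0 and 3.9 mmol/L for several hours contributes no time in hypoglycemia and is classed as non-persistent.

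**Working it through.** **Step 1: classify the same glucose values under both rules.** SAP 10.1 says CGM data arrive in mg/dL and are divided by 18.0182 and rounded to three decimals. I assume that the device reports whole mg/dL.

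| mg/dL | mmol/L | SAP 7.4 | Tables 7 and 8, if the lowest value of a reported event |
|---|---|---|---|
| 54 | 54/18.0182 = 2.997 | hypoglycemia | Grade 2 |
| 55 | 3.052 | euglycemia | Grade 1 |
| 63 | 3.496 | euglycemia | Grade 1 |
| 70 | 3.885 | euglycemia | Grade 1 |
| 71 | 3.940 | euglycemia | not graded |
| 160 | 8.880 | euglycemia | not graded |
| 161 | 8.935 | hyperglycemia | not graded |

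The overlap is 55 to 70 mg/dL, which is 16 whole values. CGM euglycemia runs from 55 to 160 mg/dL, which is 106 values. The overlap is 16/106 = 15% of the euglycemia range, or (3.9 − 3.0)/(8.9 − 3.0) = 0.9/5.9 = 15% on the mmol/L scale. That is a share of the range, not of the time.

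**Step 2: the end points.** At exactly 3.0, SAP 7.4 says hypoglycemia and Tables 7 and 8 say Grade 1, so both treat it as hypoglycemia. At exactly 3.9 there is no grade. The affected interval is strictly above 3.0 and below 3.9 mmol/L. No whole mg/dL sensor value converts to 3.0 (54 gives 2.997, 55 gives 3.052), so the choice between ≤3.0 and <3.0 makes no difference to the CGM data.

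**Step 3: how much time could be involved.** The documents give no CGM distribution, so this step rests on assumptions: lognormal glucose, mean m from 7.5 to 9.0 mmol/L, CV from 30 to 36%, and complete wear over days 2 to 8 (7 × 24 = 168 h). With σ² = ln(1 + CV²) and μ = ln(m) − σ²/2:

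- time ≤3.0 = 168 × Φ((ln 3.0 − μ)/σ)
- time in band = 168 × [Φ((ln 3.9 − μ)/σ) − Φ((ln 3.0 − μ)/σ)]

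| Mean, CV | μ, σ | Time ≤3.0 | Time >3.0 to <3.9 | Ratio |
|---|---|---|---|---|
| 7.5, 36% | 1.954, 0.349 | 1.20 h | 6.31 h | 5 |
| 7.5, 30% | 1.972, 0.294 | 0.25 h | 2.90 h | 12 |
| 9.0, 36% | 2.136, 0.349 | 0.25 h | 1.97 h | 8 |
| 9.0, 30% | 2.154, 0.294 | 0.03 h | 0.55 h | 20 |

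These are the four corners of the assumed range. The band holds roughly 5 to 20 times the time counted as hypoglycemia. As a share of modelled time in euglycemia it is small: 0.55/91.2 = 0.6% at the last corner and 6.31/124.3 = 5.1% at the first.

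**Step 4: follow the time measure into 7.3 item 7.** Take an event with sensor values of 60 mg/dL (3.330 mmol/L) for three hours. The 7.4 indicator is 0 at every reading, so the event contributes 0 h. Since 0 h is less than 1 h, it is non-persistent. If time below 3.9 mmol/L were used, it would contribute 3 h and be persistent.

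**The case against.** The other side has a strong case on the cut-off, and much of it stands.

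- **The 3.0 mmol/L cut is deliberate.** It is used for CGM time (7.4), CGM events (11.7.3.1, with a cited source) and measured hypoglycemic adverse events (7.3 item 6). It also falls at the Grade 1/2 boundary of Appendix 2, as does the 8.9 mmol/L cut for fasting hyperglycemia. One could say that the middle category simply means neither Grade 2 low nor Grade 2 high. This supports keeping the cut. It does not support calling the middle category euglycemia.
- **Tables 7 and 8 do not classify readings.** A reader might infer that any fingerstick of 3.5 mmol/L is hypoglycemia while the same sensor value is not. The SAP does not say that: the tables grade only events already reported as hypoglycemic, from the lowest value on the CRF page. Blood and interstitial glucose also differ. These points justify separate tables, but not the label.
- **The two sources can be compared at 3.0.** A reader might infer that CGM and adverse event results cannot be set side by side. They can, because measured events and CGM use the same threshold. What is missing is a CGM counterpart to the Grade 1 row.
- **Protocol Table 3 is not evidence here.** Its target level, "71 – 130 mg/dL (> 3.9 – 7.2 mmol/L) (Target Level", belongs to a dose-adjustment grid on fasting values averaged over three days. It does not define how single 15-minute sensor values should be classed.
- **A real downward shift would seldom be wholly invisible.** If the whole distribution moves down, time at or below 3.0 rises too. The blind spot is confined to time that stays above 3.0.
- **The ratio is fragile.** The value of 20 has a denominator of 0.03 h, about 2 minutes, which is less than one 15-minute reading.
- **The output is exploratory and descriptive.** No test depends on it.

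**Conclusion.** The point holds as an inconsistency of labelling and reporting. SAP 7.4 places sensor glucose above 3.0 and below 3.9 mmol/L in euglycemia, although the SAP's own event grading treats that band as Grade 1 hypoglycemia, and no reason is given. The classification result needs only the SAP's definitions and its unit conversion; the list of 16 values also assumes whole mg/dL. The time figures (0.03 to 1.2 h at or below 3.0 against 0.55 to 6.3 h in the band, per 168 h) are illustrations under assumed distributions and say nothing about this trial's data.

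The effect is limited to the exploratory CGM time tables and the persistent/non-persistent summary. The primary immunogenicity and key secondary HbA1c conclusions are untouched. The documents do not support a wider reading in which the ≤3.0 mmol/L definitions are themselves wrong and need rewriting. The change is worth making because it needs no new data and lets the CGM tables show the mild band.

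**What to change.** In SAP 7.4 and 11.7.3.2:

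1. Keep time in hypoglycemia at ≤3.0 mmol/L as defined.
2. Report time >3.0 and <3.9 mmol/L as its own CGM category.
3. Define time in euglycemia as ≥3.9 and <8.9 mmol/L.
4. Add total time <3.9 mmol/L.

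In SAP 7.3 item 7, state which time measure decides whether an event is persistent (≤3.0 or <3.9 mmol/L), or report the classification under both.

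Leave the ≤3.0 mmol/L thresholds in 7.3 item 6, 7.4 and 11.7.3.1 as they are.

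The cost is SAP wording, the matching table shell and one or two extra rows in the CGM time table. Reporting persistence under both measures would add to its summary as well. The readings are already collected. Reported time in euglycemia falls slightly, by about 0.6 to 5% at the assumed corners above. Time in hypoglycemia and time in hyperglycemia do not change.

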8.1 Full Analysis Set

The Full Analysis Set (FAS) comprises all subjects whose treatment was randomly assigned. Subjects in the FAS will be grouped according to planned treatment. Most efficacy endpoints will be analyzed using the FAS based on subject's randomized treatment and not administered treatment in case it differs.

8.2 Safety Analysis Set

The Safety Analysis Set (SS) comprises all subjects whose treatment assignment was randomly assigned who receive any IP (defined in Section 7.1), even a partial dose (Gan & Lee Insulin Glargine Injection or Lantus®). Subjects in the SS will be grouped according to the actual treatment received (defined in Section 7.1). Most safety and Immunogenicity endpoints will be analyzed using the SS.

8.3 Per Protocol Analysis Set

The Per Protocol Analysis Set (PPS) comprises all subjects whose treatment was randomly assigned and who received at least 1 partial dose and do not have any important protocol deviations as defined in Section 11.3 up to visit 26 weeks of the study. Subjects in the PPS will be grouped according to actual treatment received. The PPS will be used for some sensitivity analyses (for example, the primary endpoint for immunogenicity [from Section 11.6.1.3] and HbA1c [from Section 11.7.1.3]).

A second Per Protocol Analysis Set (PPS2) will be composed of all subjects whose treatment was randomly assigned, who received at least 1 partial dose and do not have any immunogenicity-interfering important protocol deviations (IIIPD) as defined in Section 11.3 up to visit Week 26. A third Per Protocol Analysis Set (PPS3) will be composed of all subjects whose treatment assignment was randomized, who received at least 1 partial dose and do not have any efficacy-interfering important protocol deviations (EIIPD) as defined in Section 11.3 up to visit Week 26. Subjects in the PPS2 and PPS3 will be grouped according to actual treatment received. The PPS2 and PPS3 are larger and less restrictive analysis sets than the PPS and will be used for some sensitivity analyses for the primary endpoint for immunogenicity [from Section 11.6.1.3] and HbA1c [from Section 11.7.1.3], respectively.

9. Interim Analyses

There are no planned interim analyses for this study.

10. Data Review

10.1 Data Handling and Transfer

All of the data will come from the PRA Health Sciences data management group in SAS® dataset format (SAS version 9.4 or later) converted to Study Data Tabulation Model (SDTM) version 1.4 using SDTM Implementation Guide (SDTMIG) Version 3.2 following the standard Clinical Data Interchange Standard Consortium (CDISC) conventions. Analysis datasets will be created using SAS and following CDISC analysis Data Model (ADaM, version 2.1, Implementation Guide 1.1) Standards.

Medical history and AEs will be coded using MedDRA version 22.0 to assign a system organ class (SOC) and preferred term to each event. Please refer to the Data Management Plan for details.

The following vendors will be providing data:

- PDH: Abbott CGM Data received in mg/dL, will be converted at the analysis stage by dividing with conversion factor of 18.0182 to mmol/L with numbers rounded to the thousandths
- Bioclinica: Randomization assignments (contains unblinding information)
 - True randomization assignments will not be loaded into SAS until the time of unblinding for the final analysis.
- Eurofins: Central Laboratory
- WuXi: Immunogenicity

10.2 Data Screening

Beyond the data screening built into the PRA Data Management Plan, the PRA programming of analysis datasets, tables, figures, and listings (TFL) provides additional data screening. Presumed data issues will be output into SAS logs and sent to Data Management.

A first dry run around planned last subject follow-up and a second dry run before the final database lock will allow for screening prior to database lock. The second dry run TFLs will be discussed with the sponsor

in a data review meeting with blinded team to identify any data issues and seek corrections prior to the database lock. The PRA statistician and the sponsor must approve the database freeze and the final database lock.

10.3 COVID-related Database Restrictions

As of the date of this SAP version (November 12, 2020), the clinical database contains outstanding queries that could not be reconciled due to permanent site closure and/or COVID-19 related site restrictions. All subject follow-up had completed before permanent site closure or COVID-19 site restrictions were imposed; therefore, subject safety was not affected. Each of these irreconcilable data points were reviewed by cross-functional team leads, including the PRA lead statistician and the PRA medical monitor. That review found that (a) less than 1% of the subjects were associated with an irreconcilable data point (b) no PD were related to COVID-19 given that the date of last patient follow-up was on August 13, 2019, (c) the influence of the interpretation of key immunogenicity, efficacy and safety endpoints was judged to be minimal. During the remaining data monitoring activities, some of which are remote, additional resolution will continue to complete data reconciliation. These efforts will be documented as part of the database lock process and a complete listing of irreconcilable data will be provided.

11. Statistical Methods

In general, categorical variables will be summarized using counts and percentages. Percentages will be rounded to one decimal place, except 100% will be displayed without any decimal places and percentages will not be displayed for zero counts. Continuous variables will be summarized using the number of observations (n), mean, and standard deviation, median, minimum, 25th, and 75th percentiles, and maximum. The median, minimum, 25th, and 75th percentiles, and maximum values will be displayed to the same level of precision as the raw data, the mean to a further decimal place and the standard deviation to two additional decimal places to a maximum of four. All summaries will be presented by treatment groups as well as the total if not mentioned otherwise. Tables presented by scheduled time point will include scheduled visits: Day 1 (Baseline), Week 2, Week 4, Week 8, week 12, Week 20, and Week 26 (the end of treatment (EOT) visit) where assessment applies.

Any subject who discontinues from treatment before visit Week 26 (Visit 9) will have the Visit 9 procedures performed for their EOT visit. This will be captured in the CRF under visit Week 26 and will be presented by scheduled time point tables together with Week 26 results for subjects who completed the study. Whereas no visit window will be applied for most of the visit, visit window will be considered for Week 12 or 26 visit AIA assessment only (and visit window will be considered for Week 26 visit HbA1c assessment only) if the visit is within the visit window (week 12 \pm 1 week or week 26 \pm 4 weeks). Subjects are encouraged to come back for assessments at Week 12 and Week 26 even if they have discontinued treatment early.

Subjects treated according to previous protocol version who have data recorded at visits > visit Week 26, will have those data listed only.

11.1 Pooling of Sites

Because the efficacy analyses will not be performed or stratified by site, all sites will be pooled. However, for the safety analysis described in Section 11.8.1, sites with fewer than 8 subjects will be pooled. A table in the demographic section of the appendix (Section 14) will summarize the subjects by pooled-site assignment for this HbA1c safety analysis.

11.2 Subject Disposition

The following information will be summarized for subject disposition in the FAS:

- Number and percentage of subjects in each analysis set

- Number of subjects screened and a breakdown of screen fail reasons
- Number and percentage of subjects randomized in each site
- Number and percentage of subjects randomized by pooled site
- Number and percentage of subjects who completed the comparative portion (Visit 2-9) of the study, together with the number and percentage of subjects who withdrew from the study prematurely and a breakdown of the corresponding reasons for withdrawal by discontinuation category as recorded in the End of Study CRF page
- Time from first dose of IP to early discontinuation (also as a Kaplan-Meier plot)

For subject discontinuation where the reason is recorded as 'Subject withdrawal' or 'Other' in the CRF, additional details could be captured in the clinical trial management system (CTMS) and may be summarized manually and discussed in the clinical study report. The main discontinuation categories captured in the CRF may also be manually summarized in the clinical study report by sub-categories recorded in the CTMS as follows:

- The 'Adverse Event' category may be divided into 'Adverse Event' and 'Death'.
- The 'Withdrawal by Subject' category may be divided into 12 sub-categories: 'Non-IP AE', 'Doctor advice', 'Drug switch', 'Protocol procedures', 'Protocol device', 'Higher hypoglycemia', 'Job related', 'Visit schedule', 'Move', 'Personal reason', 'Weight gain' and 'No information'.

The 'Non-compliance with Protocol' category may be divided into 'Protocol non-compliance' and 'Subject not eligible.'

A listing of subjects' randomization number, and their actual versus randomized treatment group for all the subjects in the FAS will be provided.

